9.1.2 Correlative study

- *Biologic rationale*

Activation of the hedgehog pathway in cancer may result of three mechanisms:

- loss-of-function mutations in Patched 1 (PTCH1) or gain-of-function mutations in Smoothed (SMOH) leading to constitutive Hedgehog (Hh) pathway activation as described in basal cell carcinoma and medulloblastoma.

- autocrine activation in which tumour cells produce and respond to Hedgehog ligand. Pathway activation may occur in all tumour cells or in a small number of tumour stem cells.

- paracrine model in which tumour cells produce Hedgehog ligand and surrounding stromal cells respond by growth factor; VEGF, vascular endothelial growth factor

Autocrine pathway is the sole described mechanism of hedgehog activation in chondrosarcomas (Tiet et al., 2006). However, there are no data about the mutational status of the *PTCH* and *SMO* genes in chondrosarcoma.

- *Objective*

To find predictive biomarkers of clinical benefit from GDC-0449 in patients with advanced chondrosarcomas.

- *Translational research program*

A translational research program will be conducted at the Department of Pathology, Institut Bergonié, Bordeaux, France ([name]) by using paraffin-embedded tumor samples obtained at the time of initial diagnosis or relapse.

This program will include:

- An analysis of the mutational status of *PTCH* and *SMO*

- An analysis of the expression pattern of hedgehog signaling molecules (Shh, PTCH, Smo, Gli-1, Gli-2, Gli-3) by using quantitative reverse transcription-polymerase chain reaction and immunohistochemistry (IHC) ([Tiet et al., 2006](#); [Steg et al., 2007](#)).

Concerning IHC, the staining intensity will be classified for all the proteins assessed as weak, moderate, or strong. The positive cells will be quantified as a percentage of the total number of tumor cells and assigned to one of five categories (0, <5%; 1, 5–25%; 2, 26–50%; 3, 51–75%; 4, >75%). The percentage of positivity of the tumor cells and the staining intensities were then multiplied in order to generate the IHC score ([Kim et al., 2009](#))

The 6-months clinical benefit rate will be correlated with the mutational status of *PTCH* and *SMO* and with the expression score of hedgehog signaling molecules (Shh, PTCH, Smo, Gli-1, Gli-2, Gli-3)

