| SAFETY EVALUATIONS | 
Patients will be evaluable for safety if they have received at least one dose of GDC-0449. All AEs will be graded according to the CTEP CTCAE Version 4.0. Safety profile will be continuously followed during treatment and up to 30 days after the last GDC-0449 dose or until the start of a new antitumor therapy, whichever occurs first.
 |
| TRANSLATIONAL RESEARCH PROGRAM | 
The following analyses will be done on tumor samples from patients treated with GDC-0449:
 
 - Analysis of the mutational status of PTCH and SMO - Analysis of the expression pattern of hedgehog signaling molecules (Shh, PTCH, SMO, GLI-1, GLI-2, GLI-3) by using quantitative reverse transcription-polymerase chain reaction and immunohistochemistry (IHC). 
The 6-months clinical benefit rate will be correlated with the mutational status of PTCH and SMO and with the expression score of hedgehog signaling molecules in order to identify predictive factors of clinical benefit from GDC-0449.
 |

TABLE OF CONTENTS

| | |
|---|----|
| SUMMARY OF CHANGES | I |
| SYNOPSIS | 3 |
| TABLE OF CONTENTS | 7 |
| 1. OBJECTIVES | 11 |
| 1.1. Primary Objective | 11 |
| 1.2. Secondary Objectives..... | 11 |
| 1.3. Study design and calendar..... | 11 |
| 2. BACKGROUND | 11 |
| 2.1 Study Disease..... | 11 |
| 2.2 GDC-0449..... | 12 |
| 2.3 Rationale | 21 |
| 2.4 Correlative Studies Background | 21 |
| 3. PATIENT SELECTION | 22 |
| 3.1 Eligibility Criteria | 22 |
| 3.2 Exclusion Criteria | 23 |
| 3.3 Inclusion of Women and Minorities | 24 |
| 4. REGISTRATION PROCEDURES..... | 24 |
| 4.1. General Guidelines..... | 24 |
| 4.2. Registration Process..... | 25 |
| 5. TREATMENT PLAN..... | 26 |
| 5.1 Agent Administration | 26 |
| 5.1.1 GDC-0449..... | 26 |
| 5.2 General Concomitant Medication and Supportive Care Guidelines..... | 26 |
| 5.2.1 GDC-0449..... | 26 |
| 5.3 Duration of Therapy..... | 28 |
| 5.4 Duration of Follow Up..... | 28 |
| 5.5 Criteria for removal from Study..... | 28 |
| 6. DOSING DELAYS/DOSE MODIFICATIONS | 28 |
| 7. ADVERSE EVENTS: LIST AND REPORTING REQUIREMENTS..... | 29 |
| 7.1 Comprehensive Adverse Events and Potential Risks Lists (CAEPRs) for GDC-0449 | 29 |
| 7.2 Adverse Event Characteristics [Following NCI procedures] | 33 |
| 7.3. Expedited Adverse Event Reporting [Following NCI procedures] | 33 |

| | | |
|--------------|---|----|

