1.2. Secondary Objectives

- Best overall response (as per the revised RECIST criteria 2009);
- 1- and 2-year progression-free survival;
- 1- and 2-year overall survival;
- GDC-0449 safety;
- Pharmacogenomic analysis of predictive markers of treatment outcome.

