1.3. Study design and calendar

This is single-arm phase 2 clinical trial based on two-stage Simon's design.

- Beginning of inclusions : September 2010
- Inclusion period: September 2010 to September 2012 (2 years)
- Length of patient participation: 2 years
- Study length: 4 years.

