2. BACKGROUND

2.1 Study Disease

Chondrosarcoma is the second most common primary malignancy of bone after osteosarcoma and is characterized by the production of cartilage matrix by the tumor cells ([Fletcher et al., 2002](#)). Several categories of primary chondrosarcomas have been described, including conventional, dedifferentiated, mesenchymal, and clear cell chondrosarcoma.

Conventional chondrosarcomas represent approximately 85% of all chondrosarcomas and can be categorized according to their location in bone into primary central and secondary peripheral chondrosarcomas. Central and peripheral chondrosarcomas are histologically similar, and for both, three different grades are described, which represent the best predictor of outcome. Grade I chondrosarcomas are poorly cellular, with an abundant hyaline cartilage matrix, and rarely metastasize. In contrast, grade III chondrosarcomas are highly cellular, with a mucomyxoid

matrix and mitoses, and metastasize in about 70% of cases ([Evans et al., 1977](#); [Fletcher et al., 2002](#)). The most frequent metastatic sites are the lungs, regional lymph nodes and liver. Up to 13% of recurrent chondrosarcomas exhibit a higher grade of malignancy than the original lesion, suggesting chondrosarcomas may biologically progress.

Dedifferentiated chondrosarcoma represent 9%–10% of all chondrosarcomas and is characterized from a histological point of view by conventional low-grade chondrosarcoma with abrupt transition to foci that have dedifferentiated into a higher-grade, more aggressive component ([Fletcher et al., 2002](#)). Patients with dedifferentiated chondrosarcoma are older than those with conventional lesions; the median age at diagnosis is 60 years. The prognosis is poor. Indeed, metastases occur early, are frequent and involves typically the lungs, regional lymph nodes and viscera ([Mercuri et al., 1995](#)). The 5-year survival rate is less than 10%–25%.

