13. STATISTICAL CONSIDERATIONS

13.1 Study Design/Endpoint

We will rely on a two-stage Simon's design with the 6-month clinical benefit (CR + PR + SD) rate as the primary endpoint. At six months, patients will be classified as success (Alive at 6 months AND CR/PR/ SD) or failure (dead OR alive with progression).

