13.3 Stratification Factors

No stratified analysis is foreseen.

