13.4 Analysis of Secondary Endpoints

Proportions (will be calculated and reported with their 95% confidence interval (binomial law).

Progression-free and overall survivals will be analyzed using the Kaplan-Meier method. The median survival rates will be reported with a 95% confidence interval. Median follow-up will be calculated using the reverse Kaplan-Meier method.

Duration of response will be described in responding subjects using descriptive statistics (median, extreme values, etc.).

The predictive value of biomarkers will be investigated using multivariate logistic regression (when evaluating impact on tumour response) or a Cox Proportional hazard model (when evaluating impact on time to tumour response) after checking for the proportional hazards assumption.

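### The biomarker aim is worded as prediction of benefit from GDC-0449, but one arm with stable disease counted as success can show only association with outcome under treatment

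*Combined protocol and SAP*

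**What the plan says.** The design is stated in section 1.3: "This is single-arm phase 2 clinical trial based on two-stage Simon's design". Under section 13.1, "patients will be classified as success (Alive at 6 months AND CR/PR/ SD"), so a patient whose tumour has neither shrunk nor progressed counts as a success.

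The marker aim appears in four places:

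- **Section 1.2** lists as a secondary objective "Pharmacogenomic analysis of predictive markers of treatment outcome".
- **The synopsis** (translational research program) correlates 6-month clinical benefit with *PTCH*/*SMO* mutation status and hedgehog expression scores "in order to identify predictive factors of clinical benefit from GDC-0449".
- **Section 9.1.2** repeats that correlation under the objective "To find predictive biomarkers of clinical benefit from GDC-0449 in patients with advanced chondrosarcomas".
- **Section 13.4** states: "The predictive value of biomarkers will be investigated using multivariate logistic regression" for tumour response, or a Cox model for time to tumour response. It names no covariates.

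Section 13.3 adds: "No stratified analysis is foreseen". On prognosis, section 2.1 says of conventional chondrosarcoma that "three different grades are described, which represent the best predictor of outcome". Central pathology review is planned for all patients (9.1.1), and Form C (Appendix IC) has fields for subtype and grade. The marker analysis is nowhere described as exploratory or as unable to separate prognosis from prediction.

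**The concern.** A predictive marker is one that changes the effect of the drug relative to not receiving it. A prognostic marker goes with better or worse outcome whatever the treatment. Telling them apart needs some information on outcome without the drug. Here every patient receives GDC-0449, no pre-treatment growth rate is compared with growth on treatment, and section 13.2 itself says that published survival data in advanced chondrosarcoma hardly exist.

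The endpoint sharpens the ambiguity, because slow growth alone can produce stable disease at 6 months. The population is also mixed: four subtypes are eligible, with no restriction on grade.

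At stake is what the trial may conclude on a named secondary objective. A report that followed the protocol's wording could present a marker of tumour tempo as a marker of drug sensitivity. It could also dismiss a useful marker because prognosis masked it.

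**Working it through.** **1. The plan's own figures.** The documents give no sample size, power or test level for the marker analysis. The only design figures are for the primary test (13.2): null rate 20%, target 40%, type I error 10%, power 90%, stop if 3 or fewer of 17 succeed, positive if 11 or more of 37 succeed. Exact binomial enumeration reproduces this as the optimal Simon design: type I error 0.0948, power 0.9033, probability of early stopping under the null 0.549, expected sample size 26.0. Nothing below touches that test.

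**2. What one arm identifies.** Let R1 and R0 be the success rates with and without the drug, and M+ and M− the marker groups. Then

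R1(M+) − R1(M−) = [R0(M+) − R0(M−)] + [effect in M+ − effect in M−],

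where effect = R1 − R0. The first bracket is prognostic and the second predictive. The trial observes only the left side. Suppose it sees 27.5% against 12.5%, a difference of 15 points. This fits an inactive drug with R0 of 27.5% and 12.5%. It fits equally well R0 of 12.5% in both groups with a 15-point drug effect in M+ only. More patients would not separate the two.

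**3. Illustration with no drug effect.** These inputs are assumptions, not figures from the documents, chosen so that the overall rate equals the 20% null. Half the tumours are low grade and half high grade. Success is 35% in low grade and 5% in high grade (mean 20%). The marker is positive in 75% of one grade group and 25% of the other, so half of all patients are positive.

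- Marker commoner in low grade: M+ = 0.75 × 0.35 + 0.25 × 0.05 = 0.275; M− = 0.25 × 0.35 + 0.75 × 0.05 = 0.125. Odds ratio = (0.275/0.725)/(0.125/0.875) = 2.66.
- Marker commoner in high grade: the two rates swap, and the odds ratio is 1/2.66 = 0.38.

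Varying the strength of both links:

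| Success, low/high grade | Marker split | Rates in the two marker groups | Odds ratio | Reversed |
|---|---|---|---|---|
| 30% / 10% | 65/35 | 23.0% vs 17.0% | 1.46 | 0.69 |
| 35% / 5% | 75/25 | 27.5% vs 12.5% | 2.66 | 0.38 |
| 35% / 5% | 85/15 | 30.5% vs 9.5% | 4.18 | 0.24 |

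**4. How often this would look significant.** Probability of a two-sided Fisher p below 0.05 per marker, 37 patients split 18/19, no drug effect:

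- 23% vs 17%: 4% to 6%, depending on which group has 18.
- 27.5% vs 12.5%: 13% to 18%.
- 30% vs 10% (odds ratio 3.9), higher rate in the group of 18: 30%.
- 35% vs 5% (odds ratio 10.2, a marker that tracks grade exactly), same arrangement: 65%.
- An irrelevant marker, 20% vs 20%: 3.3%.

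**5. Information available for adjustment.** Expected successes among 37 are 37 × 0.20 = 7.4 under the null and 37 × 0.40 = 14.8 at the target. Adjusting for grade and subtype is feasible only descriptively.

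**The case against.** The other side has several fair points.

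- **Entry criteria select against indolence.** Section 3.1.9 requires RECIST progression before entry, and disease must be metastatic or unresectable. Section 2.1 says that grade I tumours rarely metastasise and that metastatic disease arises especially in high-grade, mesenchymal and dedifferentiated tumours. This stands as a mitigation. It is partial, since no window or growth rate is attached to the prior progression. The 50% low-grade mix above is an assumption without support in the documents.
- **The direction is not known.** A reader might infer that an apparently favourable marker would just be a label for low grade. The documents do not support that. Section 2.3 says hedgehog signalling keeps tumour cells proliferating, so high expression could mark faster growth and push the odds ratio below 1, hiding a useful marker. Both directions must be shown.
- **Grade adjustment is not excluded.** A reader might infer from 13.3 and 13.4 that grade will be ignored. Section 13.3 rules out stratified analysis, not covariate adjustment, and 13.4 specifies a multivariable model without naming its covariates. The accurate criticism is that they are unspecified. Even full adjustment would not turn a single-arm association into a predictive effect.
- **Response is less exposed.** Indolence does not readily explain shrinkage, so the ambiguity is weaker for complete or partial response, the apparent outcome of the logistic model in 13.4. But the synopsis and 9.1.2 tie the markers to clinical benefit including stable disease.
- **Mutation status is a different kind of marker.** The illustration fits expression scores better than *PTCH*/*SMO* mutations. The identity in step 2 applies to any baseline marker.
- **No decision depends on it.** The documents attach no enrichment rule to these markers, and 1.2 speaks more loosely of treatment outcome. This limits the consequence but does not make the wording in 9.1.2 and the synopsis attainable.

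**Conclusion.** The concern holds as a limit on what may be claimed. The synopsis, 9.1.2 and 13.4 promise predictive markers of benefit from the drug, while the design supports only association with outcome under treatment. That conclusion follows from the single arm and needs no numerical assumption; counting stable disease as benefit makes it matter more.

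The size is illustrative. With no drug effect and a 20% overall rate, odds ratios run from about 0.24 to 4.2 over the assumed grade rates and marker splits. The documents give no marker prevalence, grade mix or grade-specific 6-month rate, so neither the size nor the sign can be fixed.

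A stronger reading, that the trial will probably produce a false predictive marker, is not supported: in the central case a given marker reaches p < 0.05 in only 13% to 18% of trials. Nor does the point weaken the primary Simon test, its sample size or its decision rule.

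**What to change.** 1. In the synopsis, 1.2, 9.1.2 and 13.4, replace the predictive wording with: *explore markers associated with outcome under GDC-0449; prognostic and predictive effects cannot be separated*. State that no marker will be called predictive on the basis of this trial.
2. In 13.4, report each marker association unadjusted and again accounting for central grade and subtype from Form C, both labelled descriptive. Restricting to conventional chondrosarcoma is not a substitute, because all three grades occur within that subtype. Align 13.3 if the second analysis is stratified.
3. State which outcome each marker model uses, since 9.1.2 names clinical benefit and 13.4 names tumour response. Report complete or partial response separately from stable disease.

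The cost is a change of wording and one further analysis of data already planned for collection, with no new patients, samples or visits. The price is a more modest claim and, with about 7 to 15 successes, wide intervals in the adjusted analysis.

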10. STUDY CALENDAR

Schedules shown in the Study Calendar below are provided as an example and should be modified as appropriate.

Baseline evaluations are to be conducted within 1 week prior to start of protocol therapy.

Scans and x-rays must be done ≤ 4 weeks prior to the start of therapy. In the event that the patient's condition is deteriorating, laboratory evaluations should be repeated within 48 hours prior to initiation of the next cycle of therapy.

| | Screening | Cycle 1 | | | | | Cycle 2 | | | | | Cycle 3, n | | | | | Off treatment ^c |
|--|----------------|----------------|---------|----------|----------|----------------|---------|----------|----------|----------------|---------|------------|-----------|-----------|----------------|----------------|----------------------------|
| | | We 1 Day 1 | We 1 D8 | We 2 D15 | We 3 D21 | We 4 D28 | We 5 D8 | We 6 D15 | We 7 D21 | We 8 D28 | We 9 D8 | We 10 D15 | We 11 D21 | We 11 D28 | | | |
| GDC-0449 | | X -----X | | | | | | | | | | | | | | | |
| Informed consent | X | | | | | | | | | | | | | | | | |
| Demographics | X | | | | | | | | | | | | | | | | |
| Medical history | X | | | | | | | | | | | | | | | | |
| Concurrent meds | X | X -----X | | | | | | | | | | | | | | | |
| Physical exam | X | X | | X | | X | | | | X | | | | | X ^f | | |
| Vital signs | X | X | | X | | X | | | | X | | | | | X ^f | | |
| Height | X | | | | | | | | | | | | | | | | |
| Weight | X | X | | X | | X | | | | X | | | | | X ^f | | |
| Performance status | X | X | | X | | X | | | | X | | | | | X ^f | | |
| Hematology ^e | X | X | X | X | X | X | X | X | X | X | X | X | X | X | X | | |
| Serum chemistry ^{a,e} | X | X | X | X | X | X | X | X | X | X | X | X | X | X | X | | |
| ECG (if indicated) | X | X -----X | | | | | | | | | | | | | X | | |
| Adverse event Eval | | X -----X | | | | | | | | | | | | | X | | |
| Clinical and radiology tumor eval | X | | | | | | | | | X ^d | | | | | | | |
| B-HCG | X ^b | X ^b | | | | X ^b | | | | X ^b | | | | | X ^b | X ^c | |
| Serological testing for hepatitis A, B and C | X | | | | | | | | | | | | | | | | |

A: *GDC-0449*: Dose as assigned; oral daily administration at the same time every day
a: Albumin, alkaline phosphatase, total bilirubin, bicarbonate, BUN, calcium, magnesium, chloride, creatinine, glucose, LDH, phosphorus, potassium, total protein, SGOT [AST], SGPT [ALT], sodium, CPK
b: Serum or urine test 7 days prior to the first dose of GDC-0449 administration. Pregnancy test must be administered 24 hours prior to the start of therapy (serum) and at least once every month thereafter (serum or urine).
c: Off-treatment evaluation.
d: Tumor measurements are repeated every 8 weeks. Documentation (radiology) must be provided for patients removed from study for progressive disease. Beyond 48 months of treatment without evidence of progressive disease, radiological tumor assessment will be performed every 3 months.
e: After 6 cycles, blood test will be performed every two weeks (week 2 and week 4). Beyond 48 months of treatment blood test will be performed every 3 months.
f: After 25 cycles, physical exam (vital signs, weight, performance status) will be performed/evaluated every 3 months
Baseline evaluations are to be conducted within one week prior to start of protocol therapy.
Scans and X-rays must be done ≤ 4 weeks prior to the start of therapy.

11. MEASUREMENT OF EFFECT

11.1 Antitumor Effect – Solid Tumors

For the purposes of this study, patients should be re-evaluated for response every 8 weeks. In addition to a baseline scan, confirmatory scans should also be obtained 4 weeks following initial documentation of objective response.

Response and progression will be evaluated in this study using the new international criteria proposed by the revised Response Evaluation Criteria in Solid Tumors (RECIST) guideline (version 1.1) [*Eur J Ca* 45:228-247, 2009.]. Changes in only the largest diameter (unidimensional measurement) of the tumor lesions are used in the RECIST criteria.

11.1.1 Definitions

Evaluable for toxicity: All patients will be evaluable for toxicity from the time of their first treatment with GDC-0449.

Evaluable for objective response: Only those patients who have measurable disease present at baseline and have received at least one complete or two incomplete cycle of therapy will be included in the main analysis of the response rate.

11.1.2 Disease Parameters

Measurable disease. Measurable lesions are defined as those that can be accurately measured in at least one dimension (longest diameter to be recorded) as ≥ 20 mm by chest x-ray, as ≥ 10 mm with CT scan, or ≥ 10 mm with calipers by clinical exam. All tumor measurements must be recorded in millimeters (or decimal fractions of centimeters).

Note: Tumor lesions that are situated in a previously irradiated area are not considered measurable.

Malignant lymph nodes. To be considered pathologically enlarged and measurable, a lymph node must be ≥ 15 mm in short axis when assessed by CT scan (CT scan slice thickness recommended to be no greater than 5 mm). At baseline and in follow-up, only the short axis will be measured and followed.

Non-measurable disease. All other lesions (or sites of disease), including small lesions (longest diameter < 10 mm or pathological lymph nodes with ≥ 10 to < 15 mm short axis), are considered non-measurable disease. Bone lesions, leptomeningeal disease, ascites, pleural/pericardial effusions, lymphangitis cutis/pulmonitis, inflammatory breast disease, and abdominal masses (not followed by CT or MRI), are considered as non-measurable.

Note: Cystic lesions that meet the criteria for radiographically defined simple cysts should not be considered as malignant lesions (neither measurable nor non-measurable) since they are, by definition, simple cysts.

‘Cystic lesions’ thought to represent cystic metastases can be considered as measurable lesions, if they meet the definition of measurability described above. However, if non-cystic lesions are present in the same patient, these are preferred for selection as target lesions.

Target lesions. All measurable lesions up to a maximum of 2 lesions per organ and 5 lesions in total, representative of all involved organs, should be identified as **target lesions** and recorded and measured at baseline. Target lesions should be selected on the basis of their size (lesions with the longest diameter), be representative of all involved organs, but in addition should be

those that lend themselves to reproducible repeated measurements. It may be the case that, on occasion, the largest lesion does not lend itself to reproducible measurement in which circumstance the next largest lesion which can be measured reproducibly should be selected. A sum of the diameters (longest for non-nodal lesions, short axis for nodal lesions) for all target lesions will be calculated and reported as the baseline sum diameters. If lymph nodes are to be included in the sum, then only the short axis is added into the sum. The baseline sum diameters will be used as reference to further characterize any objective tumor regression in the measurable dimension of the disease.

Non-target lesions. All other lesions (or sites of disease) including any measurable lesions over and above the 5 target lesions should be identified as **non-target lesions** and should also be recorded at baseline. Measurements of these lesions are not required, but the presence, absence, or in rare cases unequivocal progression of each should be noted throughout follow-up.

